546 via phone or email, or by completion of the appropriate eCRFs as applicable. If the form(s) are not
547 initially completed, they should be completed as soon as possible after there is sufficient information to
548 evaluate the event. All other reportable ADEs and other reportable AEs should be submitted by
549 completion on the eCRF(s) within 7 days of the site becoming aware of the event.

550 The Sponsor will notify all participating investigators of any adverse event that is serious, related, and
551 unexpected. Notification will be made within 10 working days after the Sponsor becomes aware of the
552 event.

553 Each principal investigator is responsible for reporting serious study-related adverse events and abiding
554 by any other reporting requirements specific to his/her Institutional Review Board or Ethics Committee.

555 Upon receipt of a qualifying event, the Sponsor will investigate the event to determine if a UADE has
556 occurred, and if indicated, report the results of the investigation to the HDEC, and Medsafe within 10
557 working days of the Sponsor becoming aware of the UADE. The Sponsor must determine if the UADE
558 presents an unreasonable risk to participants. If so, the Sponsor must ensure that all investigations, or
559 parts of investigations presenting that risk, are terminated as soon as possible but no later than 5 working
560 days after the Sponsor makes this determination and no later than 15 working days after first receipt
561 notice of the UADE.

562 The investigators are also required to report, without unjustified delay, all device complaints and
563 malfunctions that could have led to a UADE, including device complaints and malfunctions, irrespective
564 of whether an adverse event occurred.

565 **6.5 Safety Oversight**

566 The study Sponsor's Medical Director or Chief Medical Officer will serve as Medical Monitor, and will
567 review all reported adverse events, including all cases of severe hypoglycemia and DKA, and adverse
568 device effects that are reported during the study. SAEs typically will be reviewed within 1 working day of
569 reporting. Other AEs typically will be reviewed on a weekly basis.

570 The Medical Monitor will determine if the events require expedited reporting to Medsafe, HDEC and/or
571 all participating sites. In addition, the Medical Monitor will confirm the MedDRA code assigned and
572 adjudicate events as specified in the safety management plan for relatedness to the study procedure and
573 investigational device, assess seriousness and severity, and determine if the event the event is anticipated
574 or unanticipated. Both the investigators and Medical Monitor's assessments will be recorded, however,
575 the adjudication decision of the Medical Monitor will be used for the final classification of events,
576 including relatedness to the study procedures and/or the investigational device, for the determination of
577 safety endpoints and for all regulatory reports, product labeling, and publications or presentations. If there
578 has been a discrepancy between the Medical Monitor and Coordinating Investigator when classifying an
579 AE, it will be reported to HDEC.

580 **6.6 Stopping Criteria**

581 **6.6.1 Participant Discontinuation of Study Device**

582 In the case of an unanticipated system malfunction resulting in a severe hypoglycemia or DKA event
583 (or a malfunction that could have led to severe hypoglycemia or DKA), use of the study device will be
584 suspended for that participant while the problem is diagnosed. The UADE will be reported to HDEC and
585 Medsafe. After assessment of the problem and any correction, use of the study device will not be restarted
586 until approval is received from HDEC and Medsafe.

587 In the absence of a device malfunction, use of the study device by a participant will be discontinued if
588 any of the following occur:

- 589 • The investigator believes it is unsafe for the participant to continue on the intervention. This could be
590 due to the development of a new medical condition or worsening of an existing condition; or
591 participant behavior contrary to the indications for use of the device that imposes on the participant's
592 safety
- 593 • The participant requests that the treatment be stopped
- 594 • Participant pregnancy
- 595 • One distinct episode of DKA in the study treatment period as defined in section 6.2.4
- 596 • One distinct severe hypoglycemia event in the study treatment period as defined in section 6.2.3

597 Each DKA or severe hypoglycemia event will be reviewed by the Medical Monitor with respect to
598 determination of cause and whether the occurrence of the event can be attributed to use of the study
599 device.

600 **6.6.2 Criteria for Suspending or Stopping Overall Study**

601 In addition to the suspension of device use due to a UADE as described in section 6.6.1, study activities
602 could be similarly suspended if the manufacturer of any constituent study device requires stoppage of
603 device use for safety reasons (e.g. product recall). The affected study activities may resume if the
604 underlying problem can be corrected by a protocol or system modification that will not invalidate the
605 results obtained prior to suspension.

606 Closed-loop system use will also be suspended if there are three or more cases of severe hypoglycemia or
607 three or more cases of DKA across the entire study in participants who have initiated Tandem Freedom
608 use. The HDEC and Medsafe will be notified. After assessment of the problem and any corrections are
609 implemented, use of the closed-loop system may be restarted if approval is received from the HDEC and
610 Medsafe.

611

612

Chapter 7: Miscellaneous Considerations

613

7.1 Drugs Used as Part of the Protocol

614

Participants will use their own Humalog (insulin lispro) or Novorapid (insulin aspart) during the Run In and Treatment Period with the study devices.

616

7.2 Collection of Medical Conditions and Medications

617

Pre-Existing Conditions: Any medical condition that is either present at screening, a chronic disease, or a prior condition that could impact the participant's health during the course of the study (e.g., prior myocardial infarction or stroke) will be recorded.

620

Medical Conditions Developing During the Study: Medical conditions developing during the study will

be reviewed by the investigator for their relationship to the study device.

622

Medications: All medications in use at the time of screening or added during the course of the study will be recorded. Nutraceuticals and preventative treatment also will be recorded. Medications only taken as

needed either can be recorded when prescribed or only recorded if used during the study. Glucagon for

treatment of severe hypoglycemia will only be recorded if used during the study.

625

7.3 Prohibited Medications, Devices, Treatments, and Procedures

627

Treatment with any insulin other than Humalog or Novorapid insulin with the study pumps is not permitted. Treatment with a non-insulin glucose -lowering agent, other than metformin, is not permitted, including GLP-1 receptor agonists, Symlin, DPP-4 inhibitors, SGLT-2 inhibitors, or sulfonylureas.

630

The investigational study device (t:slim X2 insulin pump with Tandem Freedom algorithm) and study sensor and transmitter (Dexcom CGM sensor and transmitter) must be removed before magnetic resonance imaging (MRI), computed tomography (CT), X-Rays, or diathermy treatment. Participants may continue in the trial after temporarily discontinuing use if requiring one of the above.

634

7.4 Rescue Medications, Treatments, and Procedures

635

Each participant will be required to have a glucagon preparation for rescue therapy for severe hypoglycemia.

637

7.5 Pregnancy Reporting

638

If pregnancy occurs, the participant will be discontinued from the study. The occurrence of pregnancy will be reported to the Coordinating Center within seven days and to the HDEC as an Unanticipated

Problem within seven calendar days.

641

7.6 Participant Compensation

642

Participant compensation will be specified in the informed consent form.

643

7.7 Participant Withdrawal

644

Participation in the study is voluntary, and a participant may withdraw at any time. For participants who withdraw, their data will be used up until the time of withdrawal.

646

Chapter 8: Statistical Considerations

8.1 General Statistical Considerations

649 Summary statistics will be generated for all relevant variables. In the comparison of continuous variables,
650 distributions will be tested for the normality assumption. If standard parametric techniques are found to be
651 inadequate, an appropriate non-parametric technique will be used. Categorical variables will be presented
652 using frequencies and percentages and compared using differences in proportions unless stated otherwise.
653 For safety/adverse event reporting, both the number of overall events and the number of participants
654 experiencing that event will be tabulated. No corrections will be made for multiple testing procedures.

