HbA1c	Hemoglobin A1c
HDEC	Health and Disability Ethics Committees
ICH	International Conference of Harmonisation
QC	Quality Control
SAE	Serious Adverse Event
UADE	Unanticipated Adverse Device Effect

Site Principal Investigator Statement of Compliance

Protocol Identifying Number:	TP-0017517
Protocol Name:	Tandem Freedom Feasibility Trial #1
Protocol Version / Date:	2.0 / 30 APRIL 2024

The Principal Investigators (undersigned) hereby declare that they have read this protocol and agree to its contents.

The investigator agrees that the study will be conducted according to the applicable New Zealand regulations (Medsafe and Health and Disability Ethics Committee), International Conference on Harmonization (ICH) guidelines on Good Clinical Practice (GCP) and the principles of the World Medical Association Declaration of Helsinki 2008. The investigator will conduct all aspects of this study in accordance with all national, state, and local laws or regulations.

By written consent to this protocol, the investigators agree to the above and to fully co-operate with all monitoring and audits in relation to this trial by allowing direct access to all documentation, including source data, by authorized individuals representing Tandem Diabetes Care, Inc., HDEC, Medsafe New Zealand, and/or by the US Federal, State and local regulatory authorities.

Investigator Name: _____

Investigator Signature: _____

Date (DD/MMM/YYYY): _____

PROTOCOL SUMMARY

Study Sponsor	Tandem Diabetes Care, Inc.
Protocol Number	TP-0017517
Protocol Title	Tandem Freedom Feasibility Trial #1
Précis	This feasibility study is a prospective, single arm study evaluating the Tandem Freedom system compared to a Control-IQ technology run-in phase in adults with type 1 diabetes. Existing Control-IQ technology users will use Control-IQ technology at home for 1 week, then will use Tandem Freedom in a supervised hotel setting with Dexcom follow active. The goal of Tandem Freedom is to use the system without requiring meal boluses.
Products	Investigational Device: t:slim X2 insulin pump with Tandem Freedom Algorithm
Objectives	The objective of the study is to assess the feasibility of the Tandem Freedom system, by assessing safety and performance in a short-term supervised setting in adults with type 1 diabetes under direct clinical supervision.
Number of Sites	1 Clinical Site in New Zealand
Study Design	Single arm, prospective feasibility study to assess safety.

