Number of Participants	Up to 20 participants signing consent to use the study devices, with a goal that at least 10 complete the study.
Participant Population:	
Eligibility to enroll in the study will be assessed based on the following inclusion criteria:
 
 1. Age \geq18 years old 2. Diagnosis of type 1 diabetes for at least 1 year 3. Current Control-IQ user, having been prescribed Control-IQ for at least 3 months 4. HbA1c \leq 10%, recorded in the last 3 months 5. Investigator has confidence that the participant can successfully operate all study devices and is capable of adhering to the protocol, including performing the weekend hotel observed setting portion of the study. 6. Willing to use only aspart (novorapid) or lispro (humalog) insulin with the study pump, with no use of long-acting basal insulin injections, or inhaled insulin with the study pump. 7. Have current glucagon product to treat severe hypoglycemia (injectable or nasal) at home (site will provide prescription if they do not have one) 
Eligibility to enroll in the study will be assessed based on the following exclusion criteria:
 
 1. More than 1 episode of diabetic ketoacidosis (DKA) in the past 6 months 2. More than 1 episode of severe hypoglycemia (needing assistance) in the past 6 months 3. Inpatient psychiatric treatment in the past 6 months 4. For Female: Currently pregnant or planning to become pregnant during the time period of study participation 
 a. A negative pregnancy test will be required for all females of child-bearing potential b. Counseling on appropriate birth control options will be provided to all females of child-bearing potential 5. Concurrent use of any non-insulin glucose-lowering agent, other than metformin (for example, GLP-1 agonists, Symlin, DPP-4 inhibitors, SGLT-2 inhibitors, sulfonylureas). 6. Hemophilia or any other bleeding disorder 7. Hemoglobinopathy

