	
 8. History of heart, liver, lung or kidney disease determined by investigator to interfere with the study 9. History of allergic reaction to Humalog or Novorapid 10. Use of any medications determined by investigator to interfere with study 11. Significant chronic kidney disease (which could impact continuous glucose monitoring (CGM) accuracy in investigator's judgment) or hemodialysis 12. Concurrent use of any medication that could interfere with the study CGM, such as hydroxyurea 13. History of adrenal insufficiency 14. History of abnormal TSH consistent with hypothyroidism or hyperthyroidism that is not appropriately treated 15. History of gastroparesis 16. A condition, which in the opinion of the investigator or designee, would put the participant or study at risk 17. Participation in another pharmaceutical or device trial at the time of enrollment or anticipated for during the time period of study participation 18. Employed by, or having immediate family members employed by Tandem Diabetes Care, Inc., or having a direct supervisor at place of employment who is also directly involved in conducting the clinical trial (as a study investigator, coordinator, etc.); or having a first-degree relative who is directly involved in conducting the clinical trial
Participant Duration	Approximately 2 weeks

Study Endpoints	
The two study periods are:
 
 1) Control-IQ run-in period 2) The Tandem Freedom hotel observed weekend period 
Primary Endpoints for each period:
 
 1. Number of severe hypoglycemia events (with cognitive impairment such that assistance of another individual is needed for treatment) 2. Number of diabetic ketoacidosis events 3. Number of unanticipated adverse device effects 4. Number of other serious device-related adverse events 
Secondary Endpoints for each period:
 
 1. All device-related adverse events 2. CGM hypoglycemia outcomes 
 a. Overall % time <54 mg/dL b. Overall % time <70 mg/dL 3. Times in ranges-overall (70-180 mg/dL, >180 mg/dL, >250 mg/dL, 70-140 mg/dL) 4. Mean glucose 5. Glycemic variability (CV and SD) 6. Secondary endpoints 2 - 5 daytime and nighttime 
Due to the small sample size and feasibility nature of the study, primarily descriptive statistics will be used.

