8.2 Statistical Hypotheses

656 The primary objective of the study is assessment of safety. Therefore, there are no formal statistical
657 hypotheses associated with any of the endpoints. Outcomes will be primary descriptive in nature.

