8.3 Sample Size

659 The sample size of at least 10 participants completing the trial is required. As this is a feasibility study
660 assessing safety, this sample size is for a convenience sample and is not based on a power analysis.

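### Section 8.1 lets a normality test on about 10 to 20 participants choose the analysis method, so the data decide whether a mean or a pseudomedian is reported (minor, cheap to fix)

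*Combined protocol and SAP*

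**What the plan says.** Section 8.1 gives a two-step rule for comparing continuous variables. Step one: "distributions will be tested for the normality assumption. If standard parametric techniques are found to be" inadequate. Step two: "inadequate, an appropriate non-parametric technique will be used". Neither the normality test, its significance level, the fallback method, nor the quantity tested (period values or within-person differences) is named.

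On sample size, section 8.3 states that "The sample size of at least 10 participants completing the trial is required" and that this "sample size is for a convenience sample and is not based on a power analysis". The Protocol Summary allows "Up to 20 participants signing consent to use the study devices, with a goal that at least 10 complete the study". The analysed number therefore lies between about 10 and 20.

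The Protocol Summary describes the design as "Single arm, prospective feasibility study to assess safety", and its précis sets the Tandem Freedom system against the Control-IQ run-in. Any comparison is thus within participant. The continuous outcomes are the secondary CGM endpoints of section 8.4. On inference, section 8.2 says there are no formal "hypotheses associated with any of the endpoints. Outcomes will be primary descriptive in nature", and the Protocol Summary adds: "Due to the small sample size and feasibility nature of the study, primarily descriptive statistics will be used".

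**The concern.** Several CGM endpoints (% time <3.0, <3.9 and >13.9 mmol/L) are bounded at zero and likely to be right-skewed. With about 10 people a normality test has little power, so a pass says little about the distribution.

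The second difficulty is the target. A t method describes a mean. A signed-rank or Hodges-Lehmann method describes a pseudomedian (the median of pairwise averages). For a skewed variable these differ, and under section 8.1 the observed data decide which one is reported. A reader of the results could not tell in advance which quantity each row of the table would estimate.

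**Working it through.** The plan gives no power, alpha, effect size, SD or confidence interval, so there is no figure to reproduce. The rule was checked by simulation.

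**Input from the documents:** n from 10 (section 8.3) to 20 (Protocol Summary).

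**Assumptions:** Shapiro-Wilk at 5%; a t 95% interval if the test passes; an exact signed-rank (Hodges-Lehmann) 95% interval if it fails; 20,000 samples per setting; the shapes shown below.

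**Step 1: power of the test (% of skewed samples detected)**

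| Shape | n = 10 | n = 15 | n = 20 |
|---|---|---|---|
| Gamma, skew 1 | 14 | 21 | 30 |
| Lognormal σ 0.5, skew 1.75 | 25 | 38 | 52 |
| Exponential, skew 2 | 44 | 68 | 83 |
| Lognormal σ 1, skew 6.2 | 60 | 83 | 93 |

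At n = 10 the first three shapes are missed in 56% to 86% of samples. Lilliefors does worse on them (11%, 18%, 30%). A level with 40% exact zeros, a possible shape for % time <3.0 mmol/L, is detected in 84%.

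**Step 2: coverage on a common target (the mean), n = 10**

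Let p be the proportion of samples failing the normality test. Then:

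- two-stage = (1 − p) × (t coverage given pass) + p × (signed-rank coverage of the mean given fail)
- fixed t = (1 − p) × (t coverage given pass) + p × (t coverage given fail)

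For lognormal σ 1:

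- two-stage = 0.401 × 0.718 + 0.599 × 0.938 = 0.850
- fixed t = 0.401 × 0.718 + 0.599 × 0.918 = 0.838

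The first term is identical in both. The other shapes, two-stage against fixed t: gamma 94.0% and 94.0%; lognormal σ 0.5 92.0% and 91.9%; exponential 90.6% and 89.9%. With the pseudomedian as common target, two-stage is 94.4% to 94.9% against 94.7% to 95.2% for fixed signed-rank. The gaps are about 1 point or less.

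**Step 3: coverage on the target the rule selects, n = 10**

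own-target = (1 − p) × (t coverage of the mean given pass) + p × (signed-rank coverage of the pseudomedian given fail)

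- Lognormal σ 0.5: 0.750 × 0.902 + 0.250 × 0.981 = 0.922
- Exponential: 0.556 × 0.873 + 0.444 × 0.976 = 0.919
- Lognormal σ 1: 0.401 × 0.718 + 0.599 × 0.976 = 0.873

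Always using the signed-rank method gives 94.9%, 94.9% and 94.7%. For gamma skew 1 the rule gives 94.1%.

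**Step 4: paired differences, n = 10**

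Skewness partly cancels. For exponentials with scales 1.5 and 1, the test detects non-normality in 17% of samples and the rule covers 94.8%. With strongly unequal skew (lognormal σ 1 minus lognormal σ 0.5) own-target coverage is about 88%. With equal skew it is about 95%.

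**Step 5: larger n, with the mean as target**

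For lognormal σ 1 at n = 20:

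- two-stage = 0.071 × 0.575 + 0.929 × 0.775 = 0.761
- fixed t = 0.071 × 0.575 + 0.929 × 0.893 = 0.870

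For the exponential, two-stage against fixed t is 88.9% and 91.2% at n = 15, then 87.0% and 91.7% at n = 20. The cause is the change of target: nearly all samples now switch to an interval for the pseudomedian.

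**The case against.** The strongest reply is that the rule does little harm in this study. The primary endpoints are event counts, which the normality sentence does not touch. The CGM outcomes are secondary and descriptive, and no interval is specified anywhere. Section 8.1 switches method when parametric techniques are found inadequate; it sets no cutoff and does not say that a pass compels a t method. All of that stands, and it keeps the point minor.

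Three stronger readings are tempting, and the documents or the calculations do not support them.

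- **That pre-testing makes intervals worse than fixing the method.** In samples that pass the test, t coverage of the mean does fall to 90.2%, 87.3% and 71.8% for the three more skewed shapes. But a fixed t analysis gives the identical interval in those same samples, so the pre-test causes no loss there. The fault lies in the t interval under skewness. Over all samples at n = 10, the rule matches or slightly beats fixed t for these shapes.
- **That the test mostly misses skewness of any kind.** It detects extreme skewness in 60% of samples and the zero-heavy shape in 84%. The hypoglycemia endpoints may be the ones it flags.
- **That one endpoint will be summarised differently in the two periods.** Section 8.1 does not exclude testing by period, but its sentence concerns comparisons and does not say so.

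The step 3 contrast also needs care. Fixed signed-rank does better partly because the pseudomedian is easier to cover than the mean of a skewed variable. The result supports choosing the target in advance; it does not show the selection step to be defective on a common target.

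**Conclusion.** The point holds in a limited form. At n = 10 a passed normality test is weak evidence of normality, and the rule leaves the choice between mean and pseudomedian to the data. On the selected target, any interval reported would cover about 87% to 92% for skewed data. For paired differences it would cover about 88% with strongly unequal skew and about 94% to 95% when skew is mild or equal. A fixed signed-rank method gives about 95%. On a common target at n = 10 the loss is negligible. Towards n = 20, with the mean as target, the rule also loses to fixed t, by up to 11 points in the most skewed shape examined (76.1% against 87.0%).

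These sizes rest on assumed shapes, a 5% Shapiro-Wilk test and a signed-rank fallback, none of which the plan states. Severity is minor: a cheap improvement to secondary, descriptive reporting.

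**What to change.** In section 8.1, delete the normality pre-test and name one summary per endpoint, used in both periods:

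- **% time <3.0, <3.9, >10 and >13.9 mmol/L:** median (IQR) per period, and the median or Hodges-Lehmann paired difference (choose one).
- **Mean glucose, SD, CV, % time 3.9-10 and 3.9-7.9 mmol/L:** mean (SD) per period, and the mean paired difference.

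If intervals are reported, use signed-rank intervals for the first group when the Hodges-Lehmann difference is chosen, and t intervals for the second. State how zero and tied differences are handled.

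The cost is about two sentences. There are two drawbacks. Intervals are slightly wider if a skew-prone endpoint turns out to be normal. The exact signed-rank interval is also only approximate with zeros, ties or asymmetric differences, and zeros may be common. If 40% and 50% of people had no time below 3.0 mmol/L in the two periods (assumed, independent), each difference would be zero with probability 0.4 × 0.5 = 0.2. At least one zero would then occur in 1 − 0.8^10 = 89% of samples of 10.
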